8.1.11. Medical Outcomes Study 36-Item Short Form Health Survey

The Medical Outcomes Study 36-Item Short Form Health Survey (SF-36v2) Acute measure is a subjective, generic, health-related quality of life instrument that is patient-reported and consists of 36 questions covering 8 health domains:

- physical functioning
- bodily pain
- role limitations due to physical problems
- role limitations due to emotional problems
- general health perceptions
- mental health
- social function, and
- vitality.

Each domain is scored by summing the individual items and transforming the scores into a 0 to 100 scale with higher scores indicating better health status or functioning.

In addition, 2 summary scores, the physical component score and the mental component score, will be evaluated based on the 8 SF-36v2 Acute domains (Brazier et al. 1992; Ware and Sherbourne 1992).

8.1.12. MRI Imaging and Synovitis Score

Magnetic resonance imaging is a more sensitive, noninvasive imaging technique that can provide cross-sectional images in any plane allowing for simultaneous examination of all the components of the diarthrodial joint (including soft tissues, articular cartilage, and bone) without the need for ionizing radiation (McQueen and Dalbeth 2009). Specifically, both inflammatory changes (as represented by synovitis and osteitis) and structural changes (as represented by erosion and joint space narrowing) are characteristic features of RA that may be detected in patients by MRI imaging (Klarlund et al. 2000).

Magnetic resonance imaging scans will be conducted on hand/wrist determined by the investigator at the site, during screening and at the Week 12 visit. Screening scans will be evaluated to determine the presence of synovitis for study eligibility. Screening and Week 12 scans will be read and scored in pairs for each subject by 2 assessors at a central vendor, blinded to each subject's treatment and the temporal order of the scans. A detailed charter from the central reading laboratory will outline the MRI procedures including image acquisition, image analysis, and data transfer.

Synovitis, osteitis, bone erosion, and joint space narrowing scores are planned to be determined using the OMERACT RAMRIS system for synovitis, osteitis, and bone erosion (Østergaard et al. 2017).

8.2. Safety Assessments

Planned time points for all safety assessments are provided in the SoA.

8.2.1. Physical Examinations

A complete physical examination will be performed at the screening visit according to the SoA (Section 1.3). This examination excludes pelvic, rectal, and breast examinations unless clinically indicated.

A symptom directed physical examination will be performed at other visits, as specified in the SoA and as clinically indicated. A complete physical examination may be repeated at the investigator's discretion at any time a participant presents with physical complaints.

Investigators should pay special attention to clinical signs related to previous serious illnesses.

8.2.2. Vital Signs

For each participant, vital signs measurements should be conducted according to the SoA (Section 1.3). Vital signs include body temperature, blood pressure, and pulse rate (PR). Participants should be seated and relaxed with both feet on the floor for at least 5 minutes before measurements are taken. Blood pressure and pulse should be measured using either automated or manual equipment. If measurements are machine averaged, the average blood pressure reading should be recorded on the eCRF.

Measurements should be taken before any scheduled blood draws.

Additional vital signs may be measured at the discretion of the investigator.

8.2.3. Electrocardiograms

Single 12-lead ECG will be obtained as outlined in the SoA (Section 1.3) using an ECG machine that automatically calculates the heart rate and measures PR, and QRS and QT intervals.

8.2.4. Clinical Safety Laboratory Assessments

See Section 10.2, Appendix 2 for the list of clinical laboratory tests to be performed and to the SoA for the timing and frequency.

The investigator must review the laboratory report, document this review, and record any clinically relevant changes occurring during the study in the AE section of the CRF. The

laboratory reports must be filed with the source documents. Clinically significant abnormal laboratory findings are those that are not associated with the underlying disease, unless judged by the investigator to be more severe than expected for the participant's condition.

All laboratory tests with values considered clinically significantly abnormal during participation in the study or within approximately 30 days after the last dose of study intervention should be repeated until the values return to normal or baseline or are no longer considered clinically significant by the investigator or medical monitor.

If such values do not return to normal/baseline within a period of time judged reasonable by the investigator, the etiology should be identified and the sponsor notified.

All protocol-required laboratory assessments, as defined in Section [10.2](#), Appendix 2, must be conducted in accordance with the laboratory manual and the SoA.

If laboratory values from nonprotocol specified laboratory assessments performed at the institution's local laboratory require a change in participant management or are considered clinically significant by the investigator (e.g., SAE or AE or dose modification), then these would be reported in the AE section of the CRF.

8.2.5. Suicidal Ideation and Behavior Risk Monitoring

Participants being treated with the study intervention should be monitored appropriately and observed for suicidal ideation and behavior or any other unusual changes in behavior, especially at the beginning and end of the course of treatment, or at the time of dose changes, either increases or decreases. Consideration should be given to discontinuing the study medication in participants who experience signs of suicidal ideation or behavior, following a risk assessment.

Families and caregivers of participants being treated with the study intervention should be alerted about the need to monitor participants for the emergence of unusual changes in behavior, as well as the emergence of suicidal ideation and behavior and to report such symptoms immediately to the study investigator.

Baseline assessment of suicidal ideation and behavior and treatment emergent suicidal ideation and behavior will be monitored during Study KDAD using the C-SSRS.

C-SSRS Self-Harm Supplement and Follow-Up forms

The C-SSRS is a scale that captures the occurrence, severity, and frequency of suicidal ideation and behavior during the assessment period via a questionnaire. The scale was developed by the National Institute of Mental Health trial group (Treatment of Adolescent Suicide Attempters study) for the purpose of being counterpart to the Columbia Classification Algorithm of Suicide Assessment (C-CASA) categorization of suicidal events.

Consistent with Food and Drug Administration (FDA) regulatory guidance (FDA 2012), any occurrence of suicide-related thoughts and behaviors will be assessed as indicated in the SoA (Section [1.3](#)).

The Lilly Self-Harm Supplement should be completed every time the C-SSRS is administered. If, based on administration of the C-SSRS, it is determined that suicide-related behaviors have

occurred, then the Lilly Self-Harm Follow-Up form will be used to collect additional information to allow for a more complete assessment of these behaviors.

For this study, the C-SSRS is adapted for the assessment of the ideation and behavior categories only. The Intensity of Ideation and Lethality of Behavior sections are removed.

8.2.6. Tuberculosis Testing and Monitoring

Tuberculosis testing at screening Visit 1

Medical history will determine the lifetime risk factors for TB infection, for TB progression, and for symptoms and/or signs of active TB.

A physical examination will determine symptoms of active TB, including measurement of body temperature (Section 8.2.2) and assessment of peripheral lymph nodes.

A chest x-ray (CXR) will be interpreted and reported by a radiologist or pulmonologist, as specified in the SoA (Section 1.3). Participants do not need to have a CXR at screening if results from a CXR within 3 months prior to the study are available.

All participants with no history of LTBI or active TB, and no history of positive Mantoux tuberculin skin test (TST) using purified protein derivative (PPD) or positive *Mycobacterium tuberculosis* interferon gamma release assay (IGRA), must have either a PPD TST or IGRA for *M. tuberculosis*.

PPD TST

An induration of 5 or more millimeters is considered positive in:

- HIV-infected persons
- persons with a recent contact with a person with TB disease
- persons with fibrotic changes on chest radiograph consistent with prior TB
- persons with organ transplants
- persons who are immunosuppressed for other reasons (e.g., taking the equivalent of >15 mg/day of prednisone for 1 month or longer, taking TNF- α antagonists)

An induration of 10 or more millimeters is considered positive in all other potential clinical trial participants.

Two-step testing (repeat TST from 1 to 3 weeks after the first TST) is recommended for certain participant groups, including:

- persons receiving immunosuppressant treatment
- persons with a history of temporally remote increased risk of TB infection
- persons for whom the first test is negative, as per local public health and/or professional medical society recommendations.

IGRA for M. tuberculosis

Ensure that specimen handling, transport, timing, and laboratory procedures meet all requirements per package insert.

Diagnosed LTBI

Participants diagnosed with LTBI are excluded (Section 5.2) unless they are candidates for LTBI treatment, are treated for LTBI, and the following criteria are met:

- After receiving at least 4 weeks of appropriate LTBI therapy (as per WHO and/or the CDC guidelines), there is no evidence of hepatotoxicity (ALT/AST must remain ≤ 2 times ULN), or other treatment intolerance.
- The participant must continue and complete appropriate LTBI therapy in order to remain eligible to continue to receive study intervention.

Monitoring during the study

At a minimum, each participant will have the following documented at least every 3 months:

- Thorough history to determine any risk factors for TB infection and for TB progression, symptoms, or signs of active TB, and
- A thorough physical examination that includes assessment for signs of active TB, including measurement of body temperature and assessment of peripheral lymph nodes.

8.2.7. Hepatitis B Testing and Monitoring

Initial testing for HBV infection includes hepatitis B surface antigen (HBsAg) and hepatitis B core antibody (anti-HBc).

If...	Then...
If HBsAg is positive	the participant is excluded
If HBsAg is negative and anti-HBc is negative	the participant is not excluded
If HBsAg is negative and anti-HBc is positive	further testing for HBV DNA is required
If the screening HBV DNA is positive	the participant is excluded (see Section 5.2)

Participants who are hepatitis B core antibody-positive and HBV DNA-negative (undetectable) at Visit 1 are not excluded but will require HBV DNA monitoring every 3 months and at the participant's last visit.

The following actions should be taken in response to HBV DNA test results.

If...	Then...
If a single result is obtained with a value "below limit of quantitation"	the test should be repeated within approximately 2 weeks
If the repeat test result is "target not detected"	monitoring may resume according to the study schedule
If the participant has 2 or more test results with a value "below limit of quantitation" during the study	HBV DNA testing should be performed approximately once per month for the remainder of the study and referral to a hepatologist is recommended
If a result is obtained with a value "above limit of quantitation" at any time during the study	the participant will be permanently discontinued from the study intervention (see Section 7.1) and should be referred to a hepatology specialist immediately. In selected cases, investigators may temporarily continue study intervention in accordance with current immunomodulator management in the setting of HBV DNA positivity. This option may be considered in

If...	Then...
	consultation with the sponsor (or its designee) and after evaluation of individual participant's risks and benefits.

8.2.8. Hepatitis C Testing and Monitoring

Initial testing for HCV infection includes testing for antibodies to HCV.

If...	Then...
If anti-HCV is positive	HCV RNA testing should be performed
If HCV RNA test is negative	the participant is not excluded
If HCV RNA test is positive	the participant is excluded (see Section 5.2)

Participants who have had HCV infection and have been successfully treated, defined as a sustained virologic response (HCV RNA by PCR negative for at least 24 weeks following treatment completion) are not excluded on the basis of HCV as long as HCV RNA test is negative at screening.

If HCV RNA is detected during the study, the study drug will be permanently discontinued (Section 7.1), and the participant should receive appropriate follow-up medical care.

8.3. Adverse Events and Serious Adverse Events

Adverse events will be reported by the participant (or, when appropriate, by a caregiver, surrogate, or the participant's legally authorized representative).

The investigator and any qualified designees are responsible for detecting, documenting, and recording events that meet the definition of an AE or SAE and remain responsible for following up AEs that are serious, considered related to the study intervention or study procedures, or that caused the participant to discontinue the study intervention or the study (see Section 7).

8.3.1. Time Period and Frequency for Collecting AE and SAE Information

All SAEs will be collected from the signing of the ICF until participation in study has ended.

All AEs will be collected from the signing of the ICF until participation in study has ended.

Adverse events that begin before the start of study intervention but after signing of the ICF will be recorded on the AE CRF.

Although all AEs after signing the ICF are recorded by the site in the CRF/electronic data entry, SAE reporting to sponsor begins after the participant has signed the ICF and has received study drug. However, if an SAE occurs after signing the ICF, but prior to receiving the study intervention, it needs to be reported ONLY if it is considered reasonably possibly related to study procedures.

All SAEs will be recorded and reported to the sponsor or designee immediately and under no circumstance should this exceed 24 hours, as indicated in Section 10.3, Appendix 3. The investigator will submit any updated SAE data to the sponsor within 24 hours of it being available.

Investigators are not obligated to actively seek AEs or SAEs after conclusion of the study participation. However, if the investigator learns of any SAE, including a death, at any time after

a participant has been discharged from the study, and he/she considers the event to be reasonably related to the study intervention or study participation, the investigator must promptly notify the sponsor.

8.3.1.1. Adverse Event Monitoring with a Systematic Questionnaire

Nonleading AE collection should occur prior to the collection of the C-SSRS.

If a suicide-related event is discovered during the C-SSRS but was not captured during the nonleading AE collection, sites should not change the AE form.

If an AE is serious or leads to discontinuation, it needs to be included on the AE form and the process for reporting SAEs is followed.

8.3.2. Method of Detecting AEs and SAEs

The method of recording, evaluating, and assessing causality of AE and SAE and the procedures for completing and transmitting SAE reports are provided in Section [10.3](#), Appendix 3.

Care will be taken not to introduce bias when detecting AEs and/or SAEs. Open-ended and nonleading verbal questioning of the participant is the preferred method to inquire about AE occurrences.

8.3.3. Follow-up of AEs and SAEs

After the initial AE/SAE report, the investigator is required to proactively follow each participant at subsequent visits/contacts. All SAEs and AEs of special interest (AESIs) (as defined in Section [8.3.6](#)), will be followed until resolution, stabilization, the event is otherwise explained, or the participant is lost to follow-up (as defined in Section [7.3](#)). Further information on follow-up procedures is provided in Section [10.3](#), Appendix 3.

8.3.4. Regulatory Reporting Requirements for SAEs

Prompt notification by the investigator to the sponsor of a SAE is essential so that legal obligations and ethical responsibilities towards the safety of participants and the safety of a study intervention under clinical investigation are met.

The sponsor has a legal responsibility to notify both the local regulatory authority and other regulatory agencies about the safety of a study intervention under clinical investigation. The sponsor will comply with country-specific regulatory requirements relating to safety reporting to the regulatory authority, Institutional Review Boards (IRB)/Independent Ethics Committees (IEC), and investigators.

An investigator who receives an investigator safety report describing a SAE or other specific safety information (e.g., summary or listing of SAEs) from the sponsor will review and then file it along with the IB and will notify the IRB/IEC, if appropriate according to local requirements.

8.3.5. Pregnancy

Details of all pregnancies in female participants and female partners of male participants will be collected after the start of study intervention and until 8 weeks after the last dose.

If a pregnancy is reported, the investigator should inform the sponsor within 24 hours of learning of the pregnancy and should follow the procedures outlined in Section 10.4, Appendix 4.

Abnormal pregnancy outcomes (e.g., spontaneous abortion, fetal death, stillbirth, congenital anomalies, ectopic pregnancy) are considered SAEs.

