Clinician-Administered Tender/Swollen Joint Count (TSJC) (68/66)	X	X	X	X	X	X	X	X	X	X	X	X	X	Collected via an electronic tablet device. These joint counts will be performed by the Joint Assessor (Section 6.3). Determine prior to dosing
Physician's Global Assessment of Disease Activity (PhGADA_VAS)	X	X	X	X	X	X	X	X	X	X	X	X	X	Determine prior to dosing
Clinician-Administered Assessments (Paper)														
C-SSRS Screening/Baseline	X													Administer before any clinical assessments and dosing
C-SSRS Since Last Assessed		X	X	X	X	X	X	X	X	X	X	X	X	Administer before any clinical assessments and dosing
Self-harm Supplement Form	X	X	X	X	X	X	X	X	X	X	X	X	X	
Self-Harm Follow-Up Form	X	X	X	X	X	X	X	X	X	X	X	X	X	
Laboratory Tests and Sample Collections														
Hematology	X	X		X	X	X	X	X	X	X	X	X	X	Collect prior to dosing
Clinical Chemistry	X	X		X	X	X	X	X	X	X	X	X	X	In addition to scheduled assessments, these laboratory tests may also be performed as clinically indicated. Collect prior to dosing.

Study J1A-MC-KDAD	Screen	Period 1: Double-blind treatment					Period 2				ED	Post-treatment follow-up		Comments
Day ± Visit Tolerance	-42 to -1	1	14 ± 7	28 ± 7	56 ± 7	84 ± 7	98 ± 7	112 ± 7	140 ± 7	168 ± 7	Any	196 ± 7	252 ± 7	Visit 1 procedures may be conducted over more than 1 day as long as all tasks are completed within the tolerance window.
Week	-	2	4	8	12	14	16	20	24	-	28	36 or ETV + 12		
Visit number	V1	V2	V3	V4	V5	V6	V7	V8	V9	V10	ET	V801	V802	
Procedures														
Urinalysis	X	X			X			X		X	X		X	In addition to scheduled assessments, these laboratory tests may also be performed as clinically indicated. Collect prior to dosing.
Serum pregnancy	X													For all women of childbearing potential (Section 10.4).
Urine pregnancy (local)		X		X	X	X		X	X	X	X	X	X	Determine results prior to dosing
Follicle Stimulating Hormone (FSH)	X													For women who are considered postmenopausal to confirm postmenopausal status.
C-Reactive Protein, high-sensitivity (hsCRP)	X	X	X	X	X	X	X	X	X	X	X	X	X	Collect prior to dosing
Erythrocyte sedimentation rate (ESR)	X	X				X				X	X	X	X	Collect prior to dosing
Rheumatoid factor (RF)	X	X				X				X	X	X	X	Collect prior to dosing
Anticyclic citrullinated peptide (anti-CCP)	X	X				X				X	X	X	X	Collect prior to dosing
Soluble PD-1		X	X	X	X	X		X		X	X	X	X	Collect prior to dosing
Soluble PD-L1		X	X	X	X	X		X		X	X	X	X	Collect prior to dosing.

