The PK of LY3462817 has been evaluated following single doses (Study KDAB) and a small subset of the 75 mg multiple dose (Study KDAC) cohort. Nonlinear disposition that is characteristic of many monoclonal antibodies was observed at lower doses and the PK was approximately dose-proportional at doses equal to and greater than 30 mg. Based on noncompartmental analysis, in the dose linear range (≥ 30 mg), LY3462817 has estimated clearance of 10.9 mL/hr, volume of distribution of 3.9 L, and a terminal half-life of approximately 10 days. A comparison of exposure from the single dose 120 mg IV and SC cohorts indicates a bioavailability of approximately 60%. Across the IV cohorts, the median time to reach C_{max} ranges between 2 to 8 hours while for 120 mg SC, the median is approximately 9.5 days. Given the limited PK data in the multiple dose cohort (75 mg IV once every 4 weeks [Q4W]), results were not statistically analyzed. Additionally, in Study KDAB, receptor occupancy (RO) and sPD-1 concentrations in healthy volunteers following single IV doses of LY3462817 were collected and analyzed. Together, both are interpreted as measures of target engagement. Across all dose levels tested, RO and sPD-1 increased in both extent and duration with increasing dose level.

In Study KDAC, the 75-mg cohort (N=8) and 300-mg cohort (N=10) were fully enrolled. By the data cutoff date, some subjects had received a minimum of 2 doses, while some subjects had received a maximum of 4 doses (every-4-week dosing schedule).

A decision was made to dose escalate to 700 mg on 08 September 2020. Given the overall safety profile of LY3462817 to date, the sponsor believes the decision to dose escalate to 700 mg in Study KDAC provides sufficient safety data to initiate this study, KDAD.

A detailed description of the chemistry, pharmacology, toxicology, efficacy, and safety of LY3462817 is provided in the Investigator's Brochure (IB).

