4.1. Overall Design

This is a Phase 2, proof-of-concept, placebo-controlled, double-blind, randomized study in adult participants with moderately to severely active RA who have had an inadequate response to csDMARDs, or to bDMARDs/tsDMARDs. Participants will be administered LY3462817 or placebo IV Q4W.

Screening Period (Visit 1, Days -42 to -1)

Participants will sign the informed consent document(s) at Visit 1, prior to completion of any procedures. Participants will be evaluated for study eligibility \leq 42 days prior to the baseline visit (Visit 2).

Period 1: Double-blind Treatment (Visits 2 to 6; 12 weeks)

At the baseline visit (Visit 2), participants who fulfill the eligibility criteria will be randomized to receive LY3462817 700 mg, LY3462817 300 mg, or placebo in an allocation ratio of 2:1:1.

The double-blind treatment period will establish the clinical efficacy and safety of LY3462817. The study will be evaluated for the primary objective at the end of the double-blind treatment period.

Period 2 (Visits 6 to 10; 12 weeks)

Data from a Study KDAC interim analysis that includes Week 12 data from participants in the KDAC 700-mg cohort, must be reviewed prior to a participant proceeding to Period 2 in Study KDAD.

At Week 14, participants will be evaluated for clinical benefit.

Participants assigned to LY3462817 at baseline, and achieving low disease activity (CDAI \leq 10) at Week 14 will continue to receive LY3462817 at the randomized dose through Week 24 to assess safety and tolerability and evaluate efficacy.

All other participants at Week 14, regardless of baseline treatment assignment, will stop study drug infusions and should receive standard of care treatment at the investigator's discretion.

Posttreatment Safety Follow-up Period (Visits V801 and 802; 12 weeks)

Following Period 2, participants will be followed posttreatment for 12 weeks to assess safety, study drug exposure, and clinical disease activity measures. Participants who discontinue the study intervention per Section 7 will have their last visit at 12 weeks from the last administration of the study intervention.

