All other WOCBP must agree to use 2 forms of effective contraception, where at least 1 form is highly effective (less than 1% failure rate), for the entirety of the study.

Abstinence or contraception must continue following completion of study drug administration for at least 8 weeks or 5 half-lives, whichever is longer.

Acceptable Methods of Contraception

Highly effective methods of contraception (less than 1% failure rate) comprise, but are not limited to:

- combination oral contraceptives
- implanted contraceptives, or
- intrauterine devices.

Effective methods of contraception comprise but are not limited to male or female condoms with spermicide, diaphragms with spermicide, or cervical sponges.

Not Acceptable Methods of Contraception

Use of male and female condoms as a double barrier method is not considered acceptable due to the high failure rate when these barrier methods are combined.

Barrier protection methods without concomitant use of a spermicide are not an effective or acceptable method of contraception.

Periodic abstinence (e.g., calendar, ovulation, symptothermal, postovulation methods), declaration of abstinence just for the duration of a trial, and withdrawal are not acceptable methods of contraception.

Men

Men, regardless of their fertility status, must agree to either remain abstinent (if this is their preferred and usual lifestyle) or use condoms as well as 1 additional highly effective (less than 1% failure rate) method of contraception or effective method of contraception with nonpregnant WOCBP partners for the duration of the study and until their study drug concentrations are below the level that could result in a relevant potential exposure to a possible fetus, predicted to be 5 half-lives plus 90 days following the last dose of study intervention.

Acceptable Methods of Contraception

Highly effective methods of contraception (less than 1% failure rate) comprise, but are not limited to:

- combination oral contraceptives
- implanted contraceptives, or
- intrauterine devices.

Effective methods of contraception comprise but are not limited to diaphragms with spermicide or cervical sponges.

Men and their partners may choose to use a double-barrier method of contraception that must include use of a spermicide.

Not Acceptable Methods of Contraception

Use of male and female condoms as a double barrier method is not considered acceptable due to the high failure rate when these barrier methods are combined.

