Barrier protection methods without concomitant use of a spermicide are not an effective or acceptable method of contraception.

Periodic abstinence (e.g., calendar, ovulation, symptothermal, postovulation methods), declaration of abstinence just for the duration of a trial, and withdrawal are not acceptable methods of contraception.

Other Guidance

Men should refrain from sperm donation for the duration of the study and until their study drug concentrations are below the level that could result in a relevant potential exposure to a possible fetus, predicted to be 5 half-lives plus 90 days following the last dose of study intervention.

Collection of Pregnancy Information

Male participants with partners who become pregnant

The investigator will attempt to collect pregnancy information on any male participant's female partner who becomes pregnant while the male participant is in this study. This applies only to male participants who receive study intervention.

After obtaining the necessary signed informed consent from the pregnant female partner directly, the investigator will record pregnancy information on the appropriate form and submit it to the sponsor within 24 hours of learning of the partner's pregnancy. The female partner will also be followed to determine the outcome of the pregnancy. Information on the status of the mother and child will be forwarded to the sponsor. Generally, the follow-up will be no longer than 6 to 8 weeks following the estimated delivery date. Any termination of the pregnancy will be reported including fetal status (presence or absence of anomalies) and indication for the procedure.

Female Participants who become pregnant

The investigator will collect pregnancy information on any female participant who becomes pregnant while participating in this study. The initial information will be recorded on the appropriate form and submitted to the sponsor within 24 hours of learning of a participant's pregnancy.

The participant will be followed to determine the outcome of the pregnancy. The investigator will collect follow-up information on the participant and the neonate and the information will be forwarded to the sponsor. Generally, follow-up will not be required for longer than 6 to 8 weeks beyond the estimated delivery date. Any termination of pregnancy will be reported, including fetal status (presence or absence of anomalies) or indication for the procedure.

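### Pregnancy collection has two different end points (8 weeks after the last dose in Section 8.3.5, end of participation in Appendix 4), and for men dosed late neither covers the protocol's own fetal-exposure period of about 20 weeks

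*Protocol*

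**What the plan says.** The protocol describes pregnancy collection in two places.

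- **Section 8.3.5** states that pregnancy details for "female participants and female partners of male participants will be collected after the start of study intervention and until 8 weeks after the last dose". Once a pregnancy is reported, the investigator "should follow the procedures outlined in Section 10.4, Appendix 4".
- **Appendix 4 (Section 10.4)** sets the window by participation. For men it covers a partner "who becomes pregnant while the male participant is in this study". For women it covers "any female participant who becomes pregnant while participating in this study".

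Four other provisions bear on the point.

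- **Exposure through men.** Appendix 4 requires abstinence or contraception, and no sperm donation, until drug levels no longer give "relevant potential exposure to a possible fetus, predicted to be 5 half-lives plus 90 days following the last dose of study intervention". Section 2.2 gives a "terminal half-life of approximately 10 days".
- **Contraception for women.** Appendix 4 asks for the longer of 8 weeks or 5 half-lives after dosing. Exclusion 29 instead uses 20 weeks after the last dose for intended pregnancy or breastfeeding.
- **End of follow-up.** The Schedule of Activities places V802 at Week 36, or 12 weeks after the early termination visit, with a urine pregnancy test. Section 4.1 says participants who discontinue study drug under Section 7 "will have their last visit at 12 weeks from the last administration of the study intervention". Section 7.1 names only an early termination visit and V801 for them.
- **After participation.** Under Section 8.3.1 and Appendix 4, only SAEs judged related are reported, and the investigator need not look for them. SAP 4.6.7 lists whatever pregnancies are reported.

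**The concern.** Two things look wrong. First, a site reading Section 8.3.5 alone would stop recording pregnancies while the participant is still attending visits, whereas a site reading Appendix 4 would continue. Second, the sponsor defines a period after the last dose in which a man's exposure could matter to a fetus, but partner collection can end before that period does.

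What is at stake is a small amount of fetal-safety information on a new antibody. A partner pregnancy that begins after the man's last visit but inside the exposure period leaves no outcome record unless it leads to an SAE that the investigator hears of and judges related. A normal outcome would also be informative and would not be captured. Endpoints and efficacy analyses are unaffected.

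**Working it through.** **Inputs.** Half-life about 10 days, clearance 10.9 mL/hr and volume 3.9 L (Section 2.2). Nominal dose days 84, 112, 140 and 168 for Weeks 12, 16, 20 and 24, and V802 on Day 252, each ± 7 days (Schedule of Activities). The 8-week window (56 days) comes from Section 8.3.5, and the male period of 5 half-lives plus 90 days from Appendix 4.

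**1. Reproduce the half-life.** ln 2 × volume / clearance = 0.693 × 3900 / 10.9 = 248 h = 10.3 days. This agrees with the stated value.

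**2. Length of the male period.** 5 × 10 + 90 = 140 days = 20.0 weeks. With 10.33 days it is 141.7 days (20.2 weeks).

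**3. Compare the windows for participants followed to V802.** The 8.3.5 window ends at dose day + 56. In-study time after the last dose is 252 − dose day. The partner gap is 140 minus in-study time, or zero if that is negative. The range moves both the dose visit and V802 by up to 7 days.

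| Last dose | 8.3.5 ends | Days from then to V802 | In-study days after dose | Partner gap under Appendix 4 |
|---|---|---|---|---|
| Week 24 (Day 168) | Day 224 | 28 | 84 | 56 d (42 to 70) |
| Week 20 (Day 140) | Day 196 | 56 | 112 | 28 d (14 to 42) |
| Week 16 (Day 112) | Day 168 | 84 | 140 | 0 d (0 to 14) |
| Week 12 (Day 84) | Day 140 | 112 | 168 | 0 d |

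Taken literally, Section 8.3.5 falls 140 − 56 = 84 days (12 weeks) short of the male period whatever the last dose.

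The table assumes follow-up to Week 36. In particular, it assumes that stopping at Week 14, or switching to standard of care in Period 2 (Section 6.5.3), is not handled as a Section 7 discontinuation. If it were, the Section 4.1 figure below would apply.

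**4. Early discontinuers.** The documents give three ends of follow-up.

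- Section 4.1, 12 weeks after the last dose: 140 − 84 = 56 days.
- Schedule of Activities, termination visit plus 12 weeks: if that visit falls 0, 14 or 28 days after the last dose (my assumption), follow-up is 84, 98 or 112 days and the gap is 56, 42 or 28 days.
- Section 7.1, termination visit and V801: V801 is not dated for this group, so I give no figure. Section 7.1.2 also encourages these participants to stay in the study, which could shorten the gap.

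**5. Residual drug.** With first-order decline and a 10-day half-life, 2^−(84/10) = 0.30% remains at day 84 and 2^−(140/10) = 0.006% at day 140.

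**6. Men affected.** About 60 participants are assigned to LY3462817 (40 + 20), and only those with CDAI ≤ 10 at Week 14 are dosed after Week 12. The documents give no sex split, no expected rate of low disease activity and no count of men with partners of childbearing potential. The number cannot be derived.

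**The case against.** The strongest reply has four parts.

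- **Eight weeks is not arbitrary.** It equals the post-dose contraception period for women: the longer of 56 days and 5 × 10 = 50 days. This stands. A reader might infer that the limit is simply an error, and the documents do not support that. It has a basis for women, though none for partners, to whom Section 8.3.5 also applies it.
- **In-study pregnancies are not lost.** A site can satisfy both texts by following Appendix 4, AEs and SAEs are collected until participation ends, and the SAP lists every reported pregnancy. This stands. It is a conflict of wording, not demonstrated data loss.
- **The V802 pregnancy test proves nothing.** A test at 12 weeks can detect a conception from inside the 8-week window, and partners are not tested. This stands, so I do not rest the point on that test.
- **No rule ties collection to contraception.** Appendix 4 uses 5 half-lives plus 90 days for contraception and sperm donation only. A reader might infer that the plan breaks its own rule, and it does not. But the sponsor's stated reason for the period is possible fetal exposure, and that reason applies equally to learning the outcome if contraception fails.

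Contraception during the period, low residual drug and reporting of related SAEs all reduce the practical risk. They do not produce an outcome record.

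**Conclusion.** The point holds as a minor one. The two collection windows differ and should be made the same. Separately, partner collection under the broader rule ends before the protocol's exposure period: by about 8 weeks after a Week 24 dose and about 4 weeks after a Week 20 dose. For a Week 16 or Week 12 dose with follow-up to Week 36 there is no gap at nominal days, although visit windows can open up to 14 days after a Week 16 dose. For early discontinuers the size depends on which of three descriptions of follow-up applies.

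These figures rest on the 10-day half-life and on nominal visit days. It would be tempting to conclude that a meaningful number of pregnancies will be missed. The documents do not support that: the men concerned may be very few or none. Nothing in the primary analysis, sample size or other efficacy results changes.

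**What to change.** Put one rule in Section 8.3.5 and in the Appendix 4 collection text.

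- **Female participants:** collect through the end of participation and for at least 8 weeks after the last dose. At the same time, reconcile this with the 20 weeks in exclusion 29, or state why they differ.
- **Partners of male participants:** collect through the later of the end of participation or 5 half-lives plus 90 days (about 20 weeks) after the last dose.
- **Method:** at the last visit, instruct men still inside that period to report a partner pregnancy. Do not add a scheduled contact. After a Week 24 dose it would fall near Day 168 + 140 = 308, after V802, and because Section 4.4 defines completion and end of study by the last scheduled procedure, it would move both.

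Tying the partner rule to the last dose also removes the dependence on which end of follow-up applies to early discontinuers.

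The cost is a small amendment with IRB/IEC approval, which can be bundled with the next one. Each partner pregnancy reported would also need the partner's own signed consent and outcome follow-up, generally to 6 to 8 weeks after the estimated delivery date. No visits, samples or contraception requirements are added.
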